4.10 Safety Evaluation

All safety summaries and analyses will be based upon the Safety Set.

4.10.1 Adverse Events

AEs will be coded by System Organ Class (SOC) and Preferred Term (PT), using the Medical Dictionary for Regulatory Activities (MedDRA version 22.0).

AEs will be classified as pre-treatment AEs (PTAEs) and TEAEs, according to the period of occurrence, as follows:

- PTAEs: all AEs occurring before the first dose of IMP and not worsening after the first dose of IMP
- TEAEs: all AEs occurring or worsening after the first dose of IMP

Where dates are missing or partially missing, adverse events will be assumed to be treatment-emergent, unless there is clear evidence (through comparison of partial dates) to suggest that the adverse event started prior to the first dose of IMP. The detailed rules are described in [Appendix 2](#).

Individual PTAEs and TEAEs will be listed in subject data listings. No summary table will be provided for PTAEs.

Serious adverse event (SAEs) occurring or worsening after the first dose of IMP are defined as TESAEs.

For all TEAE tables, a subject will be counted only once for each System Organ Class (SOC) and each PT, even if the subject reported more than one event under each subcategory. Unless specified otherwise, TEAE tables will be ordered in terms of

decreasing number of subjects for SOC and then PT within the SOC in the column of “NAC 600 mg”, and then alphabetically for SOC and PT within the SOC if the frequency is tied.

For each subject and each adverse event, the worst severity recorded will be attributed and used in the by-severity summaries. Similarly, the worst causality (most related to treatment) will be attributed and used in the by-causality summaries. If severity or causality is missing, the worst case will be assumed.

An overview table will summarize the number and percentage on subject level of the following categories and by period (single and multiple dose):

- Any TEAE
- Any TEAE related to IMP
- Any severe TEAE
- Any severe TEAE, related to IMP
- Any TEAE with outcome of death
- Any TEAE with outcome of death, related to IMP
- Any TESAE
- Any TESAE, related to IMP
- Any TEAE leading to discontinuation of IMP
- Any TESAE leading to discontinuation of IMP
- Any TEAE leading to discontinuation of IMP, related to IMP
- Any TEAE leading to dose interruption

TEAE summaries will present the number and percentage of subjects reporting at least one TEAE. The following summaries will be provided:

- TEAEs by SOC and PT
- TEAEs by SOC and PT, by maximum severity
- TEAEs by SOC and PT, by maximum relationship
- TEAEs related to IMP, by SOC and PT
- TESAEs by SOC and PT
- TESAEs by SOC and PT, by maximum severity
- TESAEs by SOC and PT, by maximum relationship
- TESAEs related to IMP, by SOC, PT
- TEAE leading to IMP permanently stopped, by SOC and PT
- TEAE leading to death, by SOC and PT

The number and percentage of deaths will also be summarized.

The following by-subject AE listings will be provided:

- TEAEs
- TESAEs
- TEAEs related to IMP
- TEAEs leading to drug permanently stopped
- TEAEs leading to death
- PTAEs
- Deaths

The listings will include: subject identifier, age, sex, race, adverse event (SOC, PT, and verbatim term), period, date of onset, date of resolution, duration, severity, seriousness, action taken, outcome and causality.

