Critical demographic characteristics will be examined according to qualitative or quantitative data. Qualitative data will be summarised in contingency tables. Quantitative data will be summarised using classic descriptive statistics.

15.4 *Analysis of pharmacokinetic parameters*

15.4.1 *Descriptive pharmacokinetics*

A descriptive PK will be presented. The results will be displayed and summarised in tables and figures. Individual and mean curves (+SD at sampling times), indicating inter-subject variability, will be plotted. Data below the lower quantification limit (BLQL) will be considered as 0 in the calculations and presented as BLQL in listings and tables. As a consequence of BLQL (i.e. 0) values, calculated geometric means (if requested) could be null. For this reason, in the presence of any null value, the geometric mean will be reported as not calculated (NC).

15.5 *Safety and tolerability evaluation*

➤ AEs

AEs will be coded by System Organ Class (SOC) and Preferred Term (PT), using the Medical Dictionary for Regulatory Activities (MedDRA).

AEs will be classified as pre-treatment AEs (PTAEs) and TEAEs, according to the period of occurrence, as follows:

*Sponsor code Z7244J01
NAC 300 mg/3 mL i.v. bioavailability
Final version 3.0, 3Dec2019*

- PTAEs: all AEs occurring before the first dose of IMP and not worsening after the first dose of IMP
- TEAEs: all AEs occurring or worsening after the first dose of IMP

Individual PTAEs and TEAEs will be listed in subject data listings. No summary table will be provided for PTAEs. TEAEs will be summarised by treatment and overall. The number and percentage of subjects with any TEAE and the number of TEAEs will be tabulated by SOC and PT, seriousness, relationship to treatment and severity.

➤ **Physical examination**

Date of the physical examination, overall investigator's interpretation (as normal or abnormal and, if abnormal, clinically significant or not clinically significant) and clinically significant abnormalities (if any) will be listed.

➤ **Laboratory data**

Date/time of samples collection, overall investigator's interpretation (as normal or abnormal and, if abnormal, clinically significant or not clinically significant) and clinically significant findings (if any) will be listed. All laboratory results will be listed and a table of all the abnormal values will be presented. The overall investigator's interpretation will be summarised using tables of frequency.

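### The protocol asks for the number of TEAEs as well as the number of subjects; SAP 4.10.1 specifies subject counts only and does not declare the change

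*SAP*

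**What the plan says.** Protocol v3.0 section 15.5 (Safety and tolerability evaluation) states: "The number and percentage of subjects with any TEAE and the number of TEAEs will be tabulated by SOC and PT". The same sentence extends both quantities to seriousness, relationship to treatment and severity.

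SAP section 4.10.1 keeps the subject count and does not mention the event count:

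- The counting rule is: "For all TEAE tables, a subject will be counted only once for each System Organ Class (SOC) and each PT".
- The content of the summaries is: "TEAE summaries will present the number and percentage of subjects reporting at least one TEAE".
- The overview is: "An overview table will summarize the number and percentage on subject level of the following categories and by period (single and multiple dose").
- The by-severity and by-relationship tables use the worst value recorded.

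The ten SOC/PT summaries that follow in SAP 4.10.1 include none with an event count. Individual events go to listings: "Individual PTAEs and TEAEs will be listed in subject data listings". Those listings carry PT, period, onset and resolution dates, severity and causality.

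SAP section 1 names Protocol v3.0 as its basis. SAP section 4.12, on changes to the planned analysis, reads as not applicable. The revision history records several edits to 4.10.1, but no removal of event counts.

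**The concern.** The protocol promised a table quantity that the SAP does not specify, and the SAP says that nothing has changed. A reader of the two documents would expect event counts in the report.

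The gap bears on a question the study asks. The secondary end-point is safety and tolerability after single and after multiple dosing. Protocol section 6.3 says that hypersensitivity reactions are reported more often than gastrointestinal symptoms with i.v. use, and that some are associated with a higher infusion rate. Reactions of that kind could plausibly recur from one infusion to the next. Within a SOC/PT row, a subject who has a reaction once and a subject who has it after every infusion each contribute one.

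**Working it through.** **Text comparison**

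| Item | Protocol v3.0, 15.5 | SAP 4.10.1 |
|---|---|---|
| Subjects with TEAE, n (%) | Required | Specified |
| Number of TEAEs by SOC/PT | Required | Not specified |
| Number of TEAEs by seriousness, relationship, severity | Required | Not specified; subject-level tables, with maximum severity and relationship |
| Split by single/multiple dose | Not required (summary is by treatment and overall, and there is one treatment) | Stated for the overview only |
| Individual events | Listed | Listed, with period and onset date |

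**Infusions.** Protocol section 8.1.2 gives one dose on day 1, two on day 4, two on day 5 and one on day 6: 1 + 2 + 2 + 1 = 6 per subject, of which 1 is single-dose and 5 are multiple-dose. With 24 subjects (Protocol 15.2, SAP 4.11):

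- single-dose period: 24 × 1 = 24 infusions
- multiple-dose period: 24 × 5 = 120 infusions
- total: 24 × 6 = 144 infusions

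**Ceiling.** With at most one event of a given PT per infusion, a PT row could stand for up to 144 events but can show at most 24 subjects: 144/24 = 6. Within the multiple-dose period the ratio is 120/24 = 5. Both need the same PT in every subject at every infusion.

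**Illustration.** The documents give no per-infusion risk, so p below is assumed, constant and independent across infusions. Expected events = 144p. Expected subjects = 24 × (1 − (1 − p)^6).

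| Assumed p | Events | Subjects | Ratio |
|---|---|---|---|
| 0.01 | 1.44 | 1.40 | 1.03 |
| 0.05 | 7.2 | 6.36 | 1.13 |
| 0.10 | 14.4 | 11.25 | 1.28 |
| 0.20 | 28.8 | 17.71 | 1.63 |

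Clustering within subjects widens the gap: one subject reacting at all six infusions gives 6 events and 1 subject.

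**Comparison by period.** At p = 0.05:

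- Subjects, single-dose: 24 × 0.05 = 1.2, or 5%.
- Subjects, multiple-dose: 24 × (1 − 0.95^5) = 5.43, or 22.6%.
- Events: 24 × 0.05 = 1.2 in 24 infusions, and 120 × 0.05 = 6.0 in 120 infusions. Both are 5% per infusion.

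Subject percentages rise from 5% to 22.6%, and raw event counts rise fivefold, with no change in risk. Only events over infusions show the risk as constant.

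**The case against.** The strongest reply is that little is at stake. Safety is a secondary, descriptive end-point in 24 subjects, and no decision rule depends on these tables. Every TEAE is listed with its period and onset date, so repeats can be read off by hand. Protocol 6.3 says that adverse events are rare with NAC, and at low assumed risks events and subjects nearly coincide. The once-per-subject rule does not forbid an event column, and the table shells, which are not among the documents, may contain one. All of this stands. It limits the point to a tabulation gap in the SAP text; it does not answer the protocol's requirement to tabulate.

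The documents do not support several stronger readings that a reader might infer:

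- *Each subject counts once per table.* The rule is once per SOC and once per PT, so a subject with different PTs appears in several rows.
- *One reaction and six reactions look the same everywhere.* The overview is split by period, so a subject affected in both periods appears in both. Repeats collapse only within SOC/PT rows and within the five multiple-dose infusions.
- *A reaction that grows with repeated dosing cannot show.* If more subjects react, the multiple-dose column of the overview rises, though without PT detail.
- *Events are under-reported sixfold.* Six is a ceiling, and subject incidence is a different quantity, not an undercount of events.
- *The protocol requires SOC/PT tables by period.* It does not. The SAP revision history says that the summary of adverse events is by period as well, but the body text applies this to the overview only.

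**Conclusion.** The point holds as an undeclared mismatch: the SAP text omits a safety quantity that Protocol v3.0 section 15.5 specifies, and SAP 4.12 does not record the omission. As a result, repeat events of the same PT within a subject are recoverable from the listings but are in no specified table.

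The practical size depends on how often reactions recur, which the documents do not say. Under the assumed independent risks, the ratio of events to subjects runs from 1.03 at 1% to 1.63 at 20%; within-subject clustering would raise it, up to the ceiling of 6. The conclusion rests on the SAP text alone, because the table shells were not available. It should be corrected, but it does not threaten the study's primary pharmacokinetic results.

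**What to change.** Add a number-of-events column beside subject n (%) in the overview table and in the SOC/PT, severity, relationship and seriousness tables. In the severity and relationship tables, count each event at its own grade and causality, and keep the subject columns at the maximum.

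Wherever events are shown by period, print the number of infusions given in that period (planned 24 single-dose and 120 multiple-dose), so that more infusions are not read as more reactivity. Splitting the SOC/PT tables by period is optional.

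The SAP revision history places version 3.1, and so version 4.0, after database lock and after sponsor review of the final output. The change therefore belongs in a SAP addendum, as SAP section 1 provides. If the sponsor prefers subject counts only, the departure from Protocol 15.5 should be stated and justified there, and SAP 4.12 should no longer read as not applicable.

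The cost is re-running existing tables and writing the addendum. No new data are needed.

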4.10.2 Clinical Laboratory Evaluation

Laboratory values (hematology, biochemistry, and urinalysis) will be listed by subject and study time point including changes from baseline for continuous variables. The baseline for the laboratory values will be the results obtained on the last measurement before the first dose.

All values outside the clinical reference ranges will be flagged in the data listings. The abnormal values will be flagged with 'L' for values below the lower limit of the clinical reference range and 'H' for values above the upper limit of the clinical reference range and included in the listings. The Investigator will assess whether the values outside the clinical reference range are clinically significant and these will be reported as "abnormal, not clinically significant (NCS)" or "abnormal, clinically significant (CS)". Clinically significant laboratory values will be recorded by the Investigator as AEs.

Quantitative laboratory assessment reported as "<X", i.e. BQL, or ">X", i.e. above the upper limit of quantification, will be converted to X for the purpose of quantitative summaries, but will be presented as recorded, i.e. as "<X" or ">X" in the listings.

The toxicity grading of laboratory tests is determined based on the NCI CTCAE V4.03 ([Appendix 3](#)).

The following summaries will be provided for laboratory data:

- Absolute value and change from baseline for continuous data by scheduled time point.
- The number and percentage of subjects in each test result category for categorical data, by scheduled time point.
- Shifting from baseline of subjects with lab results evaluation as Normal, NCS, and CS, by scheduled time point.
- Shifting from baseline of subjects with lab results evaluated by NCI CTCAE V4.03 by toxicity grading and scheduled time point.

The following laboratory data listings will be provided:

- Listing of laboratory test results
- Listing of abnormal laboratory test results
- Listing of other lab tests and pregnancy tests.

4.10.3 Vital Signs, body weight, 12-Lead Electrocardiogram (ECG), and Physical Examinations

The following summaries and listings will be provided for vital signs and body weight:

- Absolute value and change from baseline of vital signs parameters and body weight with descriptive statistics, by scheduled time point.
- Listing of vital signs and body weight data.

12-Lead ECG will be performed at screening only and will not be summarized. A listing will be provided for ECG performance and interpretation.

Physical examinations will not be summarized. A listing of physical examination data will be provided with investigator's interpretation.

4.11 Determination of Sample Size

The sample size was not calculated through any statistical calculation. A sample size of 24 subjects was estimated as sufficient for the descriptive purposes of the present study. Drop-out subjects will not be replaced.

4.12 Changes in the Conduct of the Study or Planned Analysis

Not Applicable.

6 APPENDIX

APPENDIX 1 Study Schedule

ACTIVITIES	Screening	Single Dose					Multiple Dose				Final visit/ETV ¹	
		Visit	V1		V2			V3		V4		
			Day -14/-2	Day -1	Day 1	Day 2	Day 3	Day 4	Day 5	Day 6	Day 7	
Informed consent	x											
Demography and lifestyle	x											
Medical and surgical history	x											
Physical examination	x					x						x
Prior and concomitant medications	x	x	x	x	x	x	x	x	x	x	x	
Height	x											
Body Weight	x				x							x
Clinical laboratory analysis (haematology, blood chemistry, urinalysis)	x					x						x
Virology and bacteriology	x											
Serum pregnancy test (women)	x											
Urine multi-drug kit test	x	x										
Blood pressure and heart rate	x		x ³		x				x ³		x ⁴	
Alcohol breath test		x										
Urine pregnancy test (women)		x										
ECG	x											
Inclusion/exclusion criteria	x	x										
Subject eligibility	x	x										
Enrolment	x											
Confinement		x	x	x	x	x	x	x	x	x	x	
Discharge												x
Investigational product administration			x ⁵				x ⁶	x ⁶	x ⁵			
Blood sampling			x ⁷	x ⁷			x ⁸	x ⁸	x ⁷	x ⁷		

Urine sampling			x ⁹	x ⁹			x ⁹	x ⁹		
Standardised meals		x ¹⁰	x ¹¹	x ¹²	x ¹²	x ¹²	x ¹²	x ¹¹	x ¹²	
Adverse event monitoring¹³	x	x	x	x	x	x	x	x	x	x

1. *Early termination visit (ETV)*
2. *Final visit on day 8 or in case of ETV*
3. *At pre-dose and 1 h post-dose*
4. *The vital signs check at 48 h post-dose (day 8), will correspond to the final measurement*
5. *At 8:00 ± 1 h: 5-min infusion*
6. *At 8:00 ± 1 h and at 20:00 ± 1 h; 5-min infusion*
7. *At pre-dose (0) and 5 (at the end of the infusion), 8, 12, 15, 20, 25, 30, 60 min and 2, 4, 6, 8, 10, 12, 24 and 32 h post-dose*
8. *At pre-dose (0)*
9. *0-4; 4-8; 8-12, 12-24 and 24-32 h post-dose*
10. *Standardised dinner*
11. *Standardised lunch and dinner*
12. *Standardised breakfast, lunch and dinner*
13. *Adverse events monitored starting at the screening visit, immediately after informed consent, up to the final visit/ETV*

APPENDIX 2 Partial Date Conventions

Imputed dates will NOT be presented in the listings. However, in general, when calculating relative days, partial dates of ECG, laboratory data, standardized meals, physical examination, substance usage and vital sign with missing day only will be assumed to be 15th of the month, and partial dates with both missing day and month will be assumed to be June 30.

Otherwise, for partial dates of medical history, concomitant medication and procedures the following rules in the given table will be applied for each case.

Algorithm for Medical History, Prior/Concomitant Medications, Therapies or Procedures:

Start Date	Stop Date	Action
Known	Known	If stop date is prior to the date of first dose of study drug, considered as prior; if start date is on or after the date of first dose of study drug, considered as concomitant.
	Partial	The last day of the month and the last month (i.e. December) will be used if the day/month of stop date is missing. If the imputed stop date is prior to the date of first dose of study drug, considered as prior; if the imputed stop date is on or after the date of first dose of study drug, considered as concomitant.
	Missing	Considered as concomitant.
Partial	Known	The first day of the month and January will be used if the start day/month is missing. If stop date is prior to the date of first dose of study drug, considered as prior; if the stop date is on or after the date of first dose of study drug, considered as concomitant.
	Partial	The first day of the month and January will be used if the start day/month is missing. The last day of the month and the last month (i.e. December) will be used if the day/month of stop date is missing. If the imputed stop date is prior to the date of first dose of study drug, considered as prior; if the imputed stop date is on or after the date of first dose of study drug, considered as concomitant.
	Missing	The first day of the month and January will be used if the start day/month is missing. Considered as concomitant.

Start Date	Stop Date	Action
Missing	Known	If stop date is prior to the date of first dose of study drug, considered as prior; if stop date is on or after the date of first dose of study drug, considered as concomitant;
	Partial	The last day of the month and the last month (i.e. December) will be used if the day/month of stop date is missing. If the imputed stop date is prior to the date of first dose of study drug, considered as prior; if the imputed stop date is on or after the date of first dose of study drug, considered as concomitant.
	Missing	Considered as concomitant.

Algorithm for Treatment-Emergent Adverse Events:

Start/ Increase Severity Date	Stop Date	Action
Known	Known	Considered as a TEAE if start/increase severity date on or after the date of the first dose of study drug.
	Partial	Considered as a TEAE if start/increase severity date on or after the date of the first dose of study drug and on or before the last dose of study drug + 30 days. The last day of the month and the last month (i.e. December) will be used if the stop day/month is missing.
	Missing	Considered as a TEAE if start/increase severity date on or after the date of the first dose of study drug and on or before the last dose of study drug + 30 days.
Partial, but known components show that it cannot be on or after first study drug taken date.	Known	Not a TEAE. The first day of the month and January will be used if the start day/month or the increase severity day/month is missing.
	Partial	Not a TEAE. The first day of the month and January will be used if the start day/month or the increase severity day/month is missing. The last day of the month and the last month (i.e. December) will be used if the stop day/month is missing.
	Missing	Not a TEAE. The first day of the month and January will be used if the start day/month or the increase severity day/month is missing.
Partial, could be on or after first study drug taken date	Known	Considered as TEAE, if stop date is after first study drug taken date. The first study drug taken date will be used if start/increase severity date is in the same month/year with first study drug taken date, or the first day of the month and January will be used if the start day/month or the increase severity day/month is after first of study drug taken date. Considered as not TEAE, if stop date is prior to first of study drug taken date. The first day of the month and January will be used if the start day/month or the increase

Start/ Increase Severity Date	Stop Date	Action
		severity day/month is missing.
	Partial	Considered as TEAE. The first of study drug taken date will be used if start/ increase severity date is in the same month/year with first study drug taken date, or the first day of the month and January will be used if the start day/month or the increase severity day/month is after first study drug taken date. The last day of the month and the last month (i.e. December) will be used if the stop day/month is missing.
	Missing	Considered as TEAE. The first study drug taken date will be used if start/ increase severity date is in the same month/year with first study drug taken date, or the first day of the month and January will be used if the start day/month or the increase severity day/month is after first study drug taken date.
Missing	Known	Considered as TEAE if stop date is on or after the date of the first dose of study drug.
	Partial	The last day of the month and the last month (i.e. December) will be used if the stop day/month is missing. If the imputed stop date is on or after the first dose of study drug considered as a TEAE; if the year is missing, considered as a TEAE.
	Missing	Considered as a TEAE

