8 CLINICAL SUPPLIES

8.1 Treatment

All the subjects enrolled in the study will receive the same treatment with the investigational medicinal product (IMP), i.e. NAC, 300 mg/ 3 mL solution for injection, as follows:

- on day 1 at 08:00 ±1 h, one dose of 600 mg of NAC (300 + 300 mg ampoule) will be administered under fasting conditions;

After a wash-out of 3 days:

- on days 4 and 5 at 08:00 ±1 h and 20:00 ±1 h and at 08:00 ±1 on day 6, 5 doses of 600 mg of NAC (300 + 300 mg ampoule) will be administered.

8.1.1 *Description of products*

8.1.1.1 *Test product*

IMP	NAC 300 mg/ 3 mL solution for injection
Active substance	N-acetyl-L-cysteine
Manufacturer (active substance)	F.I.S. Fabbrica Italiana Sintetici S.p.A., [name] (GMP compliant)
Manufacturer (finished product)	Zambon S.p.A., [name] (GMP compliant)
Pharmaceutical form	Solution for injection
Dose	300 mg/ 3 mL
Administration route	Parenteral

The analytical certificates will be supplied with the IMP. Quali-quantitative formulation is as follows:

Each 3 mL vial (10%) contains:

- N-acetyl-L-cysteine (NAC) 300 mg
- sodium hydroxide 74 mg
- disodium edetate 3 mg
- water for injections q.s. to 3 mL

8.1.2 *Dose regimen*

Two ampoules of IMP (300 + 300 mg) corresponding to a total dose of 600 mg of NAC diluted in 10 mL of NaCl 0.9% sterile saline solution, will be administered by a 5-minute i.v. infusion.

Single dose:

One (1) dose of IMP will be administered under fasting conditions on day 1 at 08:00 ±1 h.

Multiple dose regime:

Five (5) doses of IMP will be administered twice a day (b.i.d.) on days 4 and 5 at 08:00 ±1 h and 20:00 ±1 h and one dose will be administered on day 6 at 08:00 ±1.

8.1.3 *Route and method of administration*

Each dose of IMP will be prepared by diluting the content of 2 ampoules of IMP in 10 mL of saline, as described above (§ 8.1.2), and administered to each study subject at the clinical site only by the investigator or his/her deputy.

Each dose will be infused intravenously over 5 min.

The start of infusion (not the end) will be considered as time 0.

8.1.4 *Investigational product distribution*

The IMP will be exclusively used for the present clinical study and will only be administered to the subjects enrolled in the study.

8.2 *Packaging and labelling*

The IMP primary packaging will be glass vials.

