16.6 Definition of Adverse Event causality

Causality shall be determined according to the definition of ADR given in [16.3](#).

All AE judged by either the investigator or the sponsor as having a reasonable suspected causal relationship to an investigational medicinal product qualify as adverse reactions. The causality assessment given by the investigator should not be downgraded by the sponsor.

The following binary decision for causality will be used:

- Reasonable possibility that the IMP caused the event
- No reasonable possibility that the IMP caused the event

Features supportive of an association include:

- temporal plausibility
- pharmacological properties of the drug or of the substance class
- course of the adverse event after dechallenge and, if applicable, after rechallenge
- specific tests indicating involvement of the drug in the occurrence/worsening of the adverse event
- alternative explanations

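### SAP Appendix 2 makes an adverse event with a known onset on Day 1 before the first infusion treatment-emergent, against the SAP's own definition

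*SAP*

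**What the plan says.** SAP 4.10.1 defines the two classes by the first dose: "PTAEs: all AEs occurring before the first dose of IMP and not worsening after the first dose of IMP" and "TEAEs: all AEs occurring or worsening after the first dose of IMP". Protocol version 3.0, section 15.5, gives the same split. Both documents say that PTAEs are listed only, while TEAEs are summarised in tables.

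For detailed rules, SAP 4.10.1 refers to Appendix 2, in a paragraph that begins "Where dates are missing or partially missing, adverse events will be assumed to be treatment-emergent, unless there is clear evidence". The TEAE algorithm there also has a row for events whose start and stop dates are both known. That row reads "Considered as a TEAE if start/increase severity date on or after the date of the first dose of study drug". The rows for a known start with a partial or missing stop use the same lower limit and add an upper limit of 30 days after the last dose, which has no bearing on Day 1. None of these rows mentions time of day.

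On the timing of the first infusion, protocol 8.1.2 says: "One (1) dose of IMP will be administered under fasting conditions on day 1 at 08:00 ±1 h".

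The AE listings are to show, among other fields, "period, date of onset, date of resolution, duration, severity". The overview table in SAP 4.10.1 is also split by single- and multiple-dose period. The SAP gives no rule for assigning an event to a period.

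**The concern.** The definition and the algorithm give different answers for the same fully dated event. Two programmers working from the same SAP could reach different TEAE counts, one by following 4.10.1 and the other by following Appendix 2.

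Events in the disputed window are foreseeable. Adverse events are collected from consent (protocol 16.8), and subjects are in the unit from the evening of Day -1. The pre-dose PK sample is drawn within 30 minutes before dosing, through an indwelling catheter (protocol 12.3.1). Protocol 6.5 names pain, bleeding and bruising as risks of blood draws.

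What is at stake is a reported result. Safety and tolerability are the secondary end-point of a single-arm study. A procedural event that preceded any drug would appear in the headline TEAE tables, with no control group to put it in proportion.

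The same ambiguity arises on Day 4. A blood sample is scheduled before the first infusion of the multiple-dose phase, and nothing says whether an event at that time belongs to the single- or the multiple-dose period.

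**Working it through.** The plan states no figure for this point, so the check applies both rules to the same events.

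**Inputs**
- Rule A (SAP 4.10.1, protocol 15.5): TEAE if the event occurs or worsens after the first dose.
- Rule B (SAP Appendix 2, known-start rows): TEAE if the onset or severity-increase date is on or after the first-dose date.
- First infusion: Day 1, 08:00 ± 1 h, so between 07:00 and 09:00 (protocol 8.1.2). Time 0 is the start of infusion (protocol 8.1.3).
- Planned number of subjects: 24 (SAP 4.11).

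**Classification.** Four onset times were tested with the first dose at 07:00, 08:00 and 09:00. Each event is taken not to worsen after the dose. The result was the same at all three dose times.

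| Onset | Rule A | Rule B | Agree? |
|---|---|---|---|
| Day -1, 22:00 | PTAE | PTAE | yes |
| Day 1, 00:30 | PTAE | TEAE | no |
| Day 1, 30 min before dose | PTAE | TEAE | no |
| Day 1, 10 min after dose | TEAE | TEAE | yes |

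The rules conflict in 2 × 3 = 6 of the 12 combinations, and every conflict is a Day 1 onset before the infusion. In each one Rule B turns a PTAE into a TEAE; the reverse never occurs. An event that starts before the dose and worsens after it is a TEAE under both rules and is not affected.

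**Effect on incidence.** If all 24 subjects are dosed, one affected subject with no other TEAE raises the overall TEAE proportion by 1/24 = 0.0417, or 4.2 percentage points. If that subject has another TEAE, overall incidence does not move, although the relevant SOC and PT rows can.

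**After the change.** Comparing onset date and time with the start of the first infusion makes both Day 1 pre-dose onsets PTAEs at all three dose times. No conflict remains for events with a recorded onset time.

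**The case against.** The best defence is scope. Appendix 2 is headed as partial-date conventions, and 4.10.1 invokes it for missing or incomplete dates, so 4.10.1 could be read as governing complete dates. This does not remove the conflict, because the appendix has an explicit row for events with both dates known and that row uses the calendar date.

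A second defence is that the consequence is limited, and this stands. The rule can only add events. A procedural event judged unrelated stays out of the table of TEAEs related to the product. The study is descriptive, with no between-arm comparison to bias.

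Third, not every Day 1 event is caught. With a partial start date that could fall on or after the first-dose date and a known stop date, the row reads "Considered as TEAE, if stop date is after first study drug taken date". An event that stops on Day 1 is not made a TEAE by that row.

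A reader might also infer several stronger claims that the documents do not support:
- **That no event can be tied to one of the two infusions on Days 4 and 5.** The listing fields named are dates, but the eCRF is not among the documents and may hold onset times. The Appendix 2 rule does not cause this gap either, since a new event on those days is a TEAE under both rules, and no analysis by infusion is planned.
- **That causality assessment is undermined.** The investigator judges causality, with "temporal plausibility" as one supporting feature, and records it in the eCRF. It is an input to the listings and is not derived from them.
- **That a reaction of a few minutes would be given a one-day duration.** The SAP states no formula for AE duration.
- **That 7 to 9 of the 24 hours of Day 1 (29-38%) are time at risk of misclassification.** That is clock time from midnight, mostly overnight. The pre-dose sample falls in the last 30 minutes, and the protocol does not say when the catheter is placed.

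**Conclusion.** The point holds for events with a known start. As written, the known-start rows of Appendix 2 give a classification that contradicts SAP 4.10.1 and protocol 15.5 for an event that begins on Day 1 before the infusion and does not worsen after it. The documents give no basis for estimating how many such events there are. The per-subject size, at most 4.2 percentage points of overall incidence, assumes that all 24 planned subjects are dosed and that the affected subject has no other TEAE.

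The SAP's silence on period assignment is a related gap at the Day 4 boundary. The documents do not show that a date-level split was intended there, so an actual misassignment cannot be claimed.

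This is a modest correction to a stated rule. It does not suggest that any reaction to the product would be missed.

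**What to change.** In the known-start rows of Appendix 2, where an onset or severity-increase time is recorded, compare date and time with the recorded start of the first infusion: at or after it is a TEAE, before it is a PTAE. Keep the present date rule only when the time is missing, which preserves the conservative default.

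State how events are assigned to the single- or multiple-dose period, using the same date-and-time comparison with the first Day 4 infusion. Show onset time in the AE listings if it was collected.

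The SAP revision history records that the database was locked before version 3.1, and the SAP Introduction sends deviations after lock to a SAP Addendum. The change belongs there. If onset times were not collected, the Addendum and the study report should say that Day 1 pre-dose events cannot be separated from TEAEs by time.

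The cost is a few lines of text, a change to the TEAE and period derivations, and a rerun of any affected tables. Infusion start times should already exist, since PK parameters use actual sampling times relative to dosing (SAP 3.2.1). No new eCRF field and no outputs by infusion number are needed.
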